7.7.2.1. Overall Summary of Adverse Events

An overall summary of AEs and SAEs will be presented. The number of events (n) and number of participants with events (n, %) will be shown for the following event subcategories:

- Any TEAE
- Any TESAE
- TEAEs leading to withdrawal from the study
- TEAEs leading to study treatment discontinuation
- Study drug-related TEAEs
- TEAEs during study drug administration

Additionally, the number and percentage of participants who died during the study will be presented. AEs and SAEs by SOC and Preferred Term. The number of AEs and the number and

percentage of participants with events will be presented by SOC and Preferred Term. Participants are counted once in each SOC and Preferred Term. Percentages will be based on the total number of treated participants in the treatment group. SAEs will be summarized similarly.

7.7.2.2. AEs and SAEs by SOC, Preferred Term, and Relationship

The number of AEs and the number and percentage of participants with events will be presented by SOC and Preferred Term as described above by relationship (related, not related). If a participant has more than 1 occurrence of an AE, the strongest relationship to study treatment will be used in the summary table. SAEs will be summarized similarly.

7.7.2.3. AEs by SOC, Preferred Term, and Severity

The number of AEs and the number and percentage of participants with events will be presented by SOC and Preferred Term as described above by severity (Grade 1, Grade 2, Grade 3, Grade 4, Grade 5). If a participant has more than 1 occurrence of an AE, the most severe occurrence will be used in the summary table.

7.7.2.4. MACE

Descriptive statistics for the number and percentage of participants with MACEs will be presented by treatment group. Pretreatment and treatment-emergent MACE rates through Day 183 (Week 26) and Day 365 (Week 52) (number per 100 patient-years) along with patient-years of follow-up and total number of MACEs will be displayed by treatment group.

7.7.2.5. Deaths and Other Significant Adverse Events

A listing of participant deaths will be produced, as well as a listing of AESI (including meningococcal infections).

7.7.3. Other Safety

7.7.3.1. Analyses for Laboratory Tests

Observed values and changes from Baseline in clinical chemistry, hematology, and urinalysis will be summarized descriptively by treatment group at Baseline and at each post-Baseline time point. For laboratory results that can be classified as normal, low, or high based on normal range values, shifts from baseline in classification will be summarized by treatment group for all study visits. For purposes of analyses, laboratory results based on standardized units will be used.

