#### Disease Characteristics

4. TMA within  $\leq$  14 days prior to Screening is associated with at least 1 of the following triggers:
  - a. Autoimmune (lupus nephritis, systemic sclerosis associated TMA [SSc-TMA])
  - b. Infection
  - c. Solid organ transplant (eg, kidney, pancreas, liver, heart, small bowel)
  - d. Drugs
  - e. Malignant hypertension

5. Confirmation of all of the following laboratory findings during the Screening Period and/or  $\leq 14$  days prior to the start of the Screening Period:
  - a. Platelet count  $< 150,000/\mu\text{L}$
  - b. Lactate dehydrogenase  $\geq 1.5 \times \text{ULN}$  and hemoglobin  $\leq \text{LLN}$  (based on age and sex)
  - c. Acute kidney injury as defined by meeting 1 or more of the following criteria (for kidney transplant recipients, the pre-TMA value is based on post-transplant eGFR):
    - Acute decline in eGFR  $\geq 50\%$  from pre-TMA value (pre-TMA value must be  $\leq 12$  months prior to Screening)
    - New acute kidney injury with an eGFR  $\leq 30 \text{ mL/min}/1.73 \text{ m}^2$
    - New initiation of dialysis due to TMA requiring  $> 1$  session and for no more than 14 days prior to Screening

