5.5. Safety Endpoints

The safety and tolerability endpoints of the study are as follows:

- 1. Incidence of adverse events (AEs) and serious adverse events (SAEs) by Week 26 and Week 52
- 2. Incidence of major adverse cardiovascular events (MACEs) by Week 26 and Week 52
- 3. Changes from Baseline in vital signs and laboratory parameters at scheduled assessments

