9.3.1. Definition of Baseline Values

Baseline for all parameters summarized during the 26-week randomized Treatment Period is defined as the last nonmissing assessment value prior to the start of study treatment (data from Screening or Day 1), prior to the date of randomization, with the exception for eGFR, for which the baseline definition is provided in Section 5.1.

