9.3.7. Analysis Values

The values being considered for analysis at a specific post-Baseline time point will be based on the analysis visit assigned to that value. If there is more than 1 nonmissing value for a specific assessment with the same analysis visit, the value used for analysis will be the one for which the calculated number of days from baseline is closest to the scheduled visit day. If 2 values have the same analysis visit and are the at same distance away from the scheduled visit day, the earlier of the 2 values will be used for analysis.

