9.3.10. Serum Creatinine and eGFR

Serum creatinine measurements are not reliable with concurrent dialysis. Therefore, all serum creatinine values obtained while a participant is on dialysis will be excluded from all analyses. The eGFR rate will be imputed with a value of 10 (in mL/min/1.73 m²) while a participant is on dialysis. A participant will be considered on dialysis from the first day of dialysis through 5 days after the end of dialysis. A participant will be considered as not requiring dialysis at a specific post-Baseline time point if they have been dialysis free for at least 14 days prior to that time point. This rule will only be applied to postbaseline assessments of serum creatinine and eGFR.

The eGFR will be calculated based on creatinine using CKD-Epi equation in patients \geq 18 years of age:

eGFR = $141 \times \min(SCr/\kappa, 1)\alpha \times \max(SCr/\kappa, 1)-1.209 \times 0.993$ Age x 1.018 [if female] × 1.159 [if Black]

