9.3.11. Platelets and Hemoglobin

Platelet and hemoglobin measurements are not reliable with concurrent red blood cell (RBC) and/or platelet transfusions. Therefore, platelet values obtained on the day of a blood transfusion of platelets through 7 days after the transfusion will be excluded from all analyses. Hemoglobin values obtained on the day of a blood transfusion of either whole blood or packed RBCs through 7 days after the transfusion will be excluded from all analyses. This rule will only be applied to postbaseline assessments of platelets and hemoglobin.

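### The by-visit low/normal/high laboratory shift table cannot show further worsening in a participant already abnormal at baseline, and two value-selection rules can drop the nadir; add a compact baseline-to-worst summary (minor)

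*SAP*

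**What the plan says.** Changes in laboratory parameters are a named safety endpoint (SAP 5.5): "Changes from Baseline in vital signs and laboratory parameters at scheduled assessments". SAP 7.7.3.1 delivers this in two ways. One is a by-visit description of values and changes, for which SAP 7.1 supplies the minimum and maximum. The other is the shift table: "classified as normal, low, or high based on normal range values, shifts from baseline in classification will be summarized by treatment group", for every study visit.

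Inclusion criterion 5 (Protocol 5.1) requires "Confirmation of all of the following laboratory findings during the Screening Period" or in the 14 days before it. The findings are platelets below 150,000/µL, LDH at least 1.5 × ULN with hemoglobin at or below LLN, and acute kidney injury. Baseline is the "last nonmissing assessment value prior to the start of study treatment" (SAP 9.3.1).

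Three rules decide which post-baseline values reach a by-visit table:

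- SAP 9.3.7: where a visit window holds several values, "the value used for analysis will be the one for which the calculated number of days from baseline is closest" to the scheduled day. On a tie the earlier value is used.
- SAP 9.3.11: "platelet values obtained on the day of a blood transfusion of platelets through 7 days after the transfusion will be excluded from all analyses". The same applies to hemoglobin after whole blood or packed red cells.
- SAP 9.3.10: "all serum creatinine values obtained while a participant is on dialysis will be excluded from all analyses". For eGFR, "The eGFR rate will be imputed with a value of 10" mL/min/1.73 m² during dialysis.

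Neither SAP 7.7.3.1 nor Protocol 9.4.2.3 plans a baseline-to-worst laboratory table. SAP 7.7.3.3 does plan one for ECGs.

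**The concern.** The entry criteria select people who are abnormal on the very parameters that define the disease. A three-class table can show such a participant staying put or improving, but it cannot show them getting worse. In a safety table, that is the direction that matters.

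The value rules add a second problem. A sharp fall is likely to prompt extra samples and a transfusion. Extra samples compete with the scheduled one for a single slot, and a transfusion removes the counts around it, including a sample drawn before the transfusion on the same day. A reader relying on the by-visit tables could therefore miss the worst value. What is at stake is the sensitivity of a descriptive safety summary. No efficacy estimate is affected.

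**Working it through.** **1. Classes left to worsen into.** For platelets and hemoglobin the adverse direction is down; for LDH it is up.

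| Baseline class | Worse classes, platelets or hemoglobin | Worse classes, LDH |
|---|---|---|
| High | 2 | 0 |
| Normal | 1 | 1 |
| Low | 0 | 2 |

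A participant still in the class that criterion 5 selects for therefore has 0 worse classes. Worsening after the value has normalized does show.

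**2. Windows.** Under SAP 9.3.6, a window starts at the midpoint with the previous visit (rounded up) and ends the day before the next window starts. The plan's own example is Day 71. Its start is (57 + 71)/2 = 64. The next start is (71 + 85)/2 = 78, so its end is 77. Days 64 to 77 agree with the SAP. The same rule applied to the laboratory visits in Protocol Table 1 gives:

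| Visit day | Window (days) | Width (days) |
|---|---|---|
| 8, 15, 22 | 5–11, 12–18, 19–25 | 7 each |
| 29 | 26–35 | 10 |
| 43, 57, 71, 85 | 36–49, 50–63, 64–77, 78–91 | 14 each |
| 99 | 92–112 | 21 |
| 127, 155 | 113–140, 141–168 | 28 each |

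One value per window is analysed. There are 12 scheduled post-baseline laboratory visits in the Treatment Period (Days 8 to 183) and 1 in follow-up (Day 365, Protocol Table 2). At most 12 + 1 = 13 values per parameter enter a participant's by-visit tables.

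**3. Transfusion exclusion.** A transfusion on day t removes days t to t + 7, which is 8 calendar days. On Day 8 it removes Days 8 to 15, so two scheduled visits are lost. The same happens on Day 15 (through Day 22) and on Day 22 (through Day 29). LDH is not covered by this rule; only the window rule applies to it.

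**4. Illustration.** These platelet values (× 10⁹/L) are assumed: baseline 80, Day 64 = 60, Day 66 = 15, Day 71 = 85. The lower limit of normal is taken as 150, the SAP's own normalization threshold.

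| Case | Value used for Day 71 visit | Tabulated change | Shift | Worst change |
|---|---|---|---|---|
| No transfusion | 85 | 85 − 80 = +5 | low to low | 15 − 80 = −65 |
| Platelets transfused Day 66 (Days 66–73 removed) | 60 | 60 − 80 = −20 | low to low | 15 − 80 = −65 |

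The value 15 reaches neither the shift table nor the by-visit minimum. A baseline-to-worst table in the same three classes would still read low to low, so the added table must use grades or numeric change.

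**5. Dialysis.** For a participant who starts dialysis, the tabulated eGFR change is 10 − baseline: −20 from 30, −5 from 15, 0 from 10, +2 from 8. It shows a fall only when baseline exceeds 10. A renal worst category should therefore rest on dialysis itself.

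**6. What cannot be computed.** The documents do not give the share still abnormal at baseline, the arm sizes or a rate of worsening, so missed worsenings cannot be counted. One participant is 1/16 = 6.25% of those enrolled.

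**The case against.** The best defence is that the plan delivers what it promises. The endpoint is change at scheduled assessments, and the Protocol promises no worst-value laboratory table.

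Other outputs also carry much of the information:

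- By-visit change with minimum and maximum shows worsening at analysed visits. Platelets, LDH, hemoglobin and eGFR are also followed as secondary endpoints (SAP 5.2).
- Clinically relevant laboratory changes are recorded as adverse events (Protocol 8.3.5), graded by CTCAE v5.0 (Protocol 10.4.3) and tabulated by arm at the most severe occurrence (SAP 7.7.2.3).
- Concomitant procedures are summarized by arm (SAP 7.2.4), and dialysis requirement is shown over time (SAP 7.3.2).
- All safety data are listed by participant (SAP 7.7), which is readable for 16 people.

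Most of this stands and sets the size of the point. Three parts of the gap remain. The by-visit minimum and maximum pass through the same window and transfusion rules. The adverse-event route depends on investigator judgement, because a disease-associated abnormality counts only if judged more severe than expected. The listings are not a by-arm summary.

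A reader might infer that the exclusion rules systematically hide harm. The documents do not support that. Transfusion raises counts and dialysis lowers creatinine, so most excluded values would look better than the true state. The clear exception is a platelet or hemoglobin sample drawn before a same-day transfusion. The dialysis rule carries less weight still, since eGFR is set to 10 and dialysis is counted separately.

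**Conclusion.** The point holds as a minor one. For platelets, hemoglobin and LDH, the shift table cannot register further worsening in anyone already in the adverse class at baseline, and SAP 9.3.7 and 9.3.11 can keep the nadir out of the by-visit tables. The mechanics are certain; how often they will matter in 16 participants is unknown.

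The conclusion is conditional on a participant still being abnormal at the last pretreatment value. A reader might infer that every participant starts at the ceiling. That does not follow: qualifying values may come from Screening or the 14 days before it, baseline is a later value for some, and hemoglobin exactly at LLN satisfies the entry criterion. Nor do the documents support a reading that laboratory deterioration would go unreported or that safety data are lost. The gap is in by-arm summary, within a study that was stopped early and is reported without treatment comparisons.

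**What to change.** Keep the planned tables. Add to SAP 7.7.3.1 one compact by-arm summary from baseline to worst post-baseline result for platelets, hemoglobin, LDH and eGFR, including unscheduled values. Use the worst CTCAE v5.0 grade where one is available, with the cut-offs printed in the SAP. Otherwise use the largest adverse change from baseline: a fall for platelets, hemoglobin and eGFR, a rise for LDH. For this safety summary only, state that:

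- all platelet and hemoglobin values in the SAP 9.3.11 transfusion window are retained and flagged;
- dialysis newly started after baseline is the worst renal category, whatever the imputed eGFR;
- participants on dialysis at baseline are shown separately.

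The cost is some SAP wording and a few descriptive tables from data already collected, in a layout already planned for ECGs. Fine multi-band shift grids would be too sparse for 16 participants. Two limits remain. A participant at the top grade at baseline still has no worse grade, which the largest-change measure avoids. SAP 9.3.11 applies only after baseline, so a fall from a transfusion-affected baseline can be overstated.

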7.7.3.2. Vital Signs

Vital signs (blood pressure, heart rate, respiratory rate, O₂ saturation, and temperature) and weight will be summarized descriptively by treatment group at Baseline and post-Baseline time point s for observed values and for changes from Baseline.

A listing of vital signs will also be presented by treatment group, participant, vital sign parameters, and visit.

7.7.3.3. Electrocardiograms

ECGs will be evaluated and summarized as normal, abnormal not clinically significant, or abnormal clinically significant. A shift from baseline to worst on-study ECG table will be presented by treatment group for ECG results. Observed values and change from Baseline in ECG intervals (PR, RR, QT, and QTc) will be summarized descriptively by treatment group at Baseline and each post-Baseline time point. QT interval will be corrected using QTcF.

A listing of ECG results will also be presented by treatment group, participant, and visit.

7.7.3.4. Immunogenicity

The incidence of ADAs to ravulizumab will be summarized descriptively by treatment group at each post-Baseline time point. In addition, the number and percentage of participants ever positive and always negative will be summarized. Any confirmed ADA-positive samples will be tested for ADA titer and the presence of neutralizing antibodies to ravulizumab, and the results will also be summarized.

7.7.3.5. Physical Examination

Adverse changes from Baseline in physical examination findings will be classified as AEs and analyzed accordingly.

7.7.3.6. COVID-19 Related Analysis

The following analysis will be performed to assess the pandemic impact of COVID-19 on the study as supplementary analyses.

Patients with COVID-19-related screen failure will be summarized and presented.

The number and proportion of participants who experience the following COVID-19 impact will be summarized by treatment group and visit in the mITT Set:

- Those who miss the scheduled visits due to COVID-19
- Those with visits modified due to COVID-19 and details relating to visit modification
- Those who miss the scheduled doses of study treatment due to COVID-19
- Those who partially or completely miss primary endpoint assessments due to COVID-19 and those who received vaccination against COVID-19 or COVID-19-related treatment

The number of missing doses per participant will be summarized by treatment group in the mITT Set.

For safety analysis, AEs, including SAEs that are considered as COVID 19 related, will be summarized.

8. **REFERENCES**

Lee C-S, Chen M-J, Chiou Y-H, Shen C-F, Wu C-Y, Chiou Y-Y. Invasive pneumococcal pneumonia is the major cause of paediatric haemolytic-uraemic syndrome in Taiwan. Nephrology. 2012;17(1):48-52.

Song D, Wu L-H, Wang F-M, et al. The spectrum of renal thrombotic microangiopathy in lupus nephritis. Arthritis Res Ther. 2013;15(1):R12-R12.

Wu L-H, Yu F, Tan Y, et al. Inclusion of renal vascular lesions in the 2003 ISN/RPS system for classifying lupus nephritis improves renal outcome predictions. Kidney Int Suppl. 2013;83(4):715-723.

9. **APPENDICES**

9.1. **Protocol Schedule of Activities**

Refer to Protocol Section 1.3 for the SoA.

9.2. Sample Size, Power, and Randomization

The planned sample size determination was based on a 2-sided Fisher's exact test performed at a 2-sided significance level of 0.05, comparing the proportion of participants achieving complete TMA response at Week 26 in participants randomized to ravulizumab versus placebo. A sample size of 100 (50 participants per treatment group) has approximately 90% power to detect a statistically significant ($p \le 0.05$) treatment difference of 35% in the proportion of responders at a 2-sided significance level of 0.05, assuming the responder rate is 35% with placebo plus BSC and 70% with ravulizumab plus BSC and an anticipated 10% dropout rate (Caires, 2012; Humphreys, 2004; Lee, 2012; Schwarz, 2010; Song, 2013; Wu, 2013).

9.3. Technical Specifications for Derived Variables

The following derived data will be calculated prior to analysis.

9.3.1. Definition of Baseline Values

Baseline for all parameters summarized during the 26-week randomized Treatment Period is defined as the last nonmissing assessment value prior to the start of study treatment (data from Screening or Day 1), prior to the date of randomization, with the exception for eGFR, for which the baseline definition is provided in Section 5.1.

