**Table 1: Schedule of Activities for Screening and 26-Week Treatment Period**

Period	Screen- ing	Treatment Period													Notes
		1	2	3	4	5	6	7	8	9	10	11	12	13	
Visit	Up to 2 W	W1	W2	W3	W4	W6	W8	W10	W12	W14	W18	W22	W26/ ED a		
Week	D -14 to -1	D1	D8 ± 2	D15 ± 2	D22 ± 2	D29 ± 2	D43 ± 2	D57 ± 2	D71 ± 3	D85 ± 3	D99 ± 3	D127 ± 3	D155 ± 3	D183 ± 3	
Days and Window															
Dispense participant safety card	X														Instruct participants to carry safety card at all times and bring it to scheduled visits
Patient Reported Outcome Questionnaires		X				X					X			X	FACIT-Fatigue, EQ-5D-5L, and KDQOL-36
Blood sample and spot urine collection for clinical laboratory tests	X d	X	X	X	X	X	X	X	X	X	X	X	X	X	Includes hematology, coagulation (screening only), clinical chemistry panels, as well as clinical complement tests and spot urine samples (Section 10.2)
Concomitant medications, nonpharmacologic therapies, and procedures		Continuous monitoring													
Adverse events	X	Continuous monitoring													
Participant safety card review		Continuous monitoring													
Medical resource utilization	X	Continuous monitoring													
Transfusion requirements		Continuous monitoring													
Dialysis requirements		Continuous monitoring													
Survival status		Continuous monitoring													
PK/PD/Immunogenicity Assessments															
Predose blood samples for PK/PD f		X		X					X			X		X	Collected anytime at Week 26 and ED Visit
Postdose blood samples for PK/PD g		X		X					X			X			
Predose blood sample for ADA		X							X			X		X	Collected anytime at Week 26 and ED Visit
Exploratory Assessments															
Blood and urine samples for exploratory biomarkers	X h	X		X			X			X		X		X	Section 8.9

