d Eligibility evaluation may be based on laboratory results obtained during the Screening Period or ≤ 14 days prior to the start of the Screening Period. Local or central laboratory results may be used to determine eligibility, with the exceptions of the ST-HUS screen and ADAMTS13 activity tests which must be performed at the central laboratory. With the exceptions of the ST-HUS screen and ADAMTS13 activity tests, if local labs are used to establish eligibility, central laboratory tests are not required at the Screening visit.

e Participants must be supine during ECG collection.

f The baseline predose sample on Day 1 will be collected within 90 minutes prior to the start of infusion. For all subsequent visits falling on dosing days, predose samples will be collected within 0.5 hours prior to the start of infusion. In order to minimize needle sticks to the participant, the predose sample may be drawn through the venous access created for the dose infusion, prior to administration of the dose.

g Samples will be collected postdose at EOI (within 0.5 hours after the EOI from the participant's opposite, noninfused arm).

h Collect blood and urine samples for exploratory biomarker and RTCA prior to therapeutic plasma exchange/plasma infusion, if applicable. Participants are prohibited from receiving therapeutic plasma exchange / plasma infusion at any time following randomization during the Treatment Period.

i For participants that provide additional informed consent for genetic testing.

Abbreviations: ADA = antidrug antibody; ADAMTS13 = a disintegrin and metalloproteinase with a thrombospondin type 1 motif, member 13; AE = adverse event; BP = blood pressure; D = day; ECG = electrocardiogram; ED = early discontinuation; EQ-5D-5L = EuroQoL 5 Dimension 5 Level; FACIT = Functional Assessment of Chronic Illness Therapy; KDQOL-36 = Kidney Disease Quality of Life instrument – 36 items; PD = pharmacodynamics; PK = pharmacokinetics; RTCA = Real Time Complement Activity; ST-HUS = Shiga toxin-related hemolytic uremic syndrome; TMA = thrombotic microangiopathy; W = Week; WOCBP = woman of childbearing potential.

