## **6.3. Measures to Minimize Bias: Randomization and Blinding**

### **6.3.1. Randomization**

Participants will be randomized on Day 1. Participants will be randomized 1:1 either to the ravulizumab treatment group or to the placebo treatment group. Randomization will be performed centrally using Interactive Response Technology (IRT).

To balance the effects of potential confounding factors between the ravulizumab and placebo arms, randomization will be stratified by baseline dialysis status (Yes versus No) and primary trigger type (autoimmune, infection, solid organ transplant, drugs, or malignant hypertension) using a dynamic allocation procedure (Pocock, 1975).

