#### **9.4.1.2.2. Analyses of Additional Secondary Endpoints**

Additional secondary endpoints defined in [Table 4](#) will be analyzed as follows:

Time to response for each individual TMA parameter during the 26-week Treatment Period will be assessed in a similar manner as time to Complete TMA Response.

The binary additional secondary endpoints will be summarized by randomized treatment group by calculating the point estimate and 2-sided 95% CI for the response rate, based on exact confidence limits using the Clopper Pearson method. Treatment comparison of the response rate at all scheduled assessments during the 26-week randomized Treatment Period will be based on Cochran-Mantel-Haenszel test stratified by randomization stratification factors.

For continuous additional secondary endpoints, MMRM model will be used and similar statistics will be provided as described above.

For all parameters summarized during the Randomized Treatment Period other than eGFR, baseline is defined as the last non-missing assessment value prior to the start of study treatment (data from Screening or Day 1, prior to date of randomization).

For participants who require dialysis, change from baseline in dialysis requirements will be summarized.

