5.2. Secondary Endpoints

The following is a list of secondary efficacy endpoints. Due to early termination of the study, there are no longer any "key secondary endpoints" with multiplicity adjustment.

- 1. Time to complete TMA response (measured in days from Day 1 to the first day that the participant satisfies the criteria for complete TMA response) during the 26-week randomized Treatment Period.
 - TMA response occurs on the first day when all components of TMA response are met simultaneously, with each component meeting the requirement at 2 separate assessments obtained at least 24 hours apart, and any measurement in between.
- 2. Achievement of hematologic response at Week 26.
- 3. Change from Baseline in eGFR at Week 26.
- 4. On dialysis at Week 26.
- 5. Time to response for each TMA parameter (Table 2) during the 26-week randomized Treatment Period
 - Hematologic response
 - Renal response
- 6. Achievement of individual component of complete TMA response at all scheduled assessments
 - Hematologic response
 - Renal response
 - At least one of the TMA parameters
- 7. Changes from Baseline in hematologic response parameters at all scheduled assessments
 - Platelets
 - LDH
 - Hemoglobin
- 8. Increase in hemoglobin at Week 26 of
 - $\geq 2 \text{ g/dL}$
 - $\geq 1 \text{ g/dL}$
- 9. Change in kidney function
 - Change from Baseline in eGFR at all scheduled assessments
 - Change from Baseline in dialysis requirement at Week 26 and Week 52
 - Duration of dialysis (for participants who had dialysis within the 26-week randomized Treatment Period or within the study)

- 10. Complete TMA response at Week 52 among participants who achieved complete TMA response during the 26-week randomized Treatment Period
- 11. Loss of TMA response during the 26-week randomized Treatment Period (for participants who achieved complete TMA response during the 26-week randomized Treatment Period)
- 12. TMA relapse during the Post-Treatment Follow-up Period (for participants who achieved complete TMA response during the 26-week randomized Treatment Period)
- 13. Change in patient-reported outcomes as measured by Functional Assessment of Chronic Illness Therapy-Fatigue (FACIT-Fatigue) at all scheduled assessments

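### The baseline rule accepts Day 1 values but also requires a date before randomization, which is itself on Day 1; the date clause should be deleted

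*SAP*

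**What the plan says.** SAP 9.3.1 defines baseline for everything except eGFR as the last nonmissing value "prior to the start of study treatment (data from Screening or Day 1), prior to the date of randomization". The date condition and its single exemption stand together there: "prior to the date of randomization, with the exception for eGFR". Protocol 9.4.1.2.2 has the same construction: "data from Screening or Day 1, prior to date of randomization".

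On timing, Protocol 6.3.1 states: "Participants will be randomized on Day 1". Table 1 of the protocol also marks randomization in the Day 1 column.

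Table 1 has a row headed "Patient Reported Outcome Questionnaires", covering "FACIT-Fatigue, EQ-5D-5L, and KDQOL-36". It is marked at Days 1, 29, 99 and 183, and its Screening cell is empty. Table 2 adds Weeks 34 and 52. SAP 5.2 lists as a secondary endpoint: "Change in patient-reported outcomes as measured by Functional Assessment of Chronic Illness Therapy-Fatigue (FACIT-Fatigue) at all scheduled assessments".

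For laboratory tests, footnote d of Table 1 says that, apart from the ST-HUS and ADAMTS13 tests, "if local labs are used to establish eligibility, central laboratory tests are not required at the Screening visit".

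eGFR has its own rule in SAP 5.1. For participants not on dialysis, it is the last nonmissing value before study treatment, with no condition tied to randomization.

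**The concern.** One half of the sentence accepts Day 1 data and the other half rejects them. A programmer has to choose which half to obey, and the SAP does not say which one governs.

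The choice matters most where Day 1 is the first scheduled measurement, because without it there is nothing to subtract. It matters less, but still matters, for platelets, LDH and hemoglobin. These are drawn at Screening and again on Day 1, and TMA can change quickly between the two. Their change from baseline is a secondary endpoint, and the hemoglobin increases of at least 1 and at least 2 g/dL at Week 26 are counted from the same baseline.

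**Working it through.** The plan gives no figure to reproduce here. The check is one of dates.

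**Inputs**
- Date of randomization = Day 1 (Protocol 6.3.1; Table 1).
- FACIT-Fatigue, EQ-5D-5L and KDQOL-36: Days 1, 29, 99, 183 (Table 1), then Weeks 34 and 52 (Table 2).
- Free and total C5: first sample on Day 1, predose (Table 1; Protocol 8.7).
- Platelets, LDH, hemoglobin: Screening (Day -14 to -1), Day 1 and later visits (Table 1).
- A change score needs both a baseline and a later value (SAP 9.3.4).
- Continuous secondary endpoints use observed data only (SAP 7.1.1).

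**Rule as written, applied by date.** A value qualifies if its date is earlier than the randomization date. For a Day 1 value the two dates are equal, so it fails.

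**Rule without the date clause.** A value qualifies if it was taken before the first infusion. A Day 1 predose value passes.

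| Measure | Scheduled candidates, literal rule | Scheduled candidates, clause removed |
|---|---|---|
| FACIT-Fatigue, EQ-5D-5L, KDQOL-36 | none | Day 1 |
| Free and total C5 | none | Day 1 predose |
| Platelets, LDH, hemoglobin | Screening only | Day 1 predose, otherwise Screening |
| eGFR | exempt (SAP 5.1) | exempt (SAP 5.1) |

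**FACIT-Fatigue count.** Scheduled post-baseline visits: 3 in the Treatment Period (Days 29, 99, 183) + 2 in follow-up (Weeks 34, 52) = 5.
- Literal rule: 0 qualifying baselines, so change is calculable at 0 of 5 visits.
- Clause removed: 1 qualifying baseline, so change is calculable at 5 of 5 visits.
- Treatment Period alone: 0 of 3 against 3 of 3. This is the safer count, because the study was to end once the last treated participant finished the 26 weeks (SAP Section 4).

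**Laboratory parameters.** The literal baseline would be dated 1 to 14 days before Day 1, which is the width of the Screening window. The documents do not report the actual intervals.

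**What the clause does not touch.** The primary endpoint uses fixed thresholds for platelets (at least 150000/µL) and LDH (no more than 1.5 × ULN), and an eGFR improvement with its own baseline (SAP 5.1). Serum ravulizumab concentration is summarized over time (SAP 7.6) and ADA as post-baseline incidence (SAP 7.7.3.4), so neither needs a baseline to subtract.

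**The case against.** The strongest reply is that nobody would read the sentence as excluding Day 1. It names Day 1 as a data source, and an exclusion would leave those words without meaning. Other sections agree. Footnote f of Table 1 and Protocol 8.7 both call the Day 1 predose PK/PD sample the baseline sample. SAP 9.3.6 counts days from baseline starting at the Day 1 visit. The note to Table 1 puts assessments before dosing on dosing days unless otherwise specified, and Protocol 8.11.1 puts the questionnaires ahead of other procedures. A program that dropped Day 1 would produce empty change tables for FACIT-Fatigue, which would be noticed at once.

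Most of this stands. A reader might infer that the plan leaves FACIT-Fatigue without a baseline. The documents do not support that as the plan's intent; it is only the outcome of one literal reading. What remains is that the written condition conflicts with the intent, and a programmer following the intent must disregard it without any instruction to do so. The laboratory fallback would also be harder to notice than an empty table, because a Screening value would usually be there to fill the gap.

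A second reply is that the clause means the moment of randomization and not the calendar day. The text says date. Even on the softer reading, the documents do not require the Day 1 predose blood draws to come before randomization, so some could still be excluded.

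A reader might also infer that laboratory baselines would be missing wherever only local screening tests were done. That is not established. Protocol Section 5 does say that analyses are planned on central results. But SAP 9.3.1 does not confine baseline to central values, and SAP 5.5.3 prefers central results only when local and central samples duplicate each other. The supportable statement is that the fallback value may be local only.

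**Conclusion.** The point holds as an internal contradiction in the baseline definition, present in both documents. Applied literally by date, it would make change from baseline incalculable for FACIT-Fatigue, EQ-5D-5L, KDQOL-36, and free and total C5. It would also replace Day 1 baselines for platelets, LDH and hemoglobin with Screening values up to 14 days older. Day 1 predose use was evidently intended.

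The practical weight is limited. It would be wrong to infer that the primary result is at risk: complete TMA response and eGFR do not use this clause. The study closed with 16 participants (SAP Section 4), and SAP 4.2 rules out hypothesis tests and inferential treatment comparisons, so no test is affected. Even so, change from baseline is the quantity to be reported for these endpoints, and in a group this small the definition should leave nothing to guess. It should be corrected before programming.

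The sizes given assume a comparison of calendar dates, randomization on Day 1 as scheduled, and no unscheduled questionnaire or C5 sample before Day 1.

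**What to change.** In SAP 9.3.1 and Protocol 9.4.1.2.2, delete the clause that ties baseline to the date of randomization. State that baseline, other than for eGFR, is the last nonmissing value before the start of the first infusion of study drug, and that Day 1 predose values count. If the protocol will not be amended again, make the change in the SAP and record it in SAP 4.2 as a clarification of the protocol text.

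The cost is one phrase in each document. No new data are needed, and no visit, endpoint or analysis method changes.
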